## 7.3. Lost to Follow up

In this study, the majority of the patients will remain at the nursing home for the whole duration of the study. Some patients will, however, leave the nursing home for home based isolation at a point in time when the SARS-CoV-2 PCR is still positive. In such cases a home based visit will be performed by site personnel, to obtain the final measures according to the SoA.

A participant will be considered lost to follow-up if unable to be contacted by the study site. Before a participant is deemed lost to follow up, the investigator or designee must make every effort to regain contact with the participant.

- The site must attempt to contact the participant and reschedule the missed visit as soon as possible and counsel the participant on the importance of maintaining the assigned visit schedule and ascertain whether or not the participant wishes to and/or should continue in the study. Where possible, telephone calls and, if necessary, a certified letter to the participant's last known mailing address or local equivalent methods should be attempted. These contact attempts should be documented in the participant's medical record.
- Should the participant continue to be unreachable, he/she will be considered to have withdrawn from the study.
- Site personnel, or an independent third party, will attempt to collect the vital status of the participant within legal and ethical boundaries for all participants randomized, including

those who did not get study intervention. Public sources may be searched for vital status information. If vital status is determined as deceased, this will be documented, and the participant will not be considered lost to follow-up.

• Discontinuation of specific sites or of the study as a whole are handled as part of Appendix 1.

## 8. Study Assessments and Procedures

## 8.1. Efficacy assessments

*The efficacy of convalescent plasma on the primary endpoint of all-cause mortality* at day 28 will be recorded from the Norwegian death registry.

*The efficacy of convalescent plasma on the secondary endpoint of all-cause mortality* at day 60 will be recorded from the Norwegian death registry.

*The efficacy of convalescent plasma on the secondary endpoint of recovery time* will be assessed by repeated respiratory tract sampling for SARS-CoV-2 PCR analyses at day 1, 3, 7, 14 and 28. The site for sampling as well as the actual sampling technique will be standardized, underscoring the importance of a uniform procedure for all participating centers. Samples will be analyzed at the participating local microbial laboratories adhering to national guidelines for this testing. All samples for a single patient will be tested at the same laboratory to reduce inter-institutional variability. Samples will furthermore be stored for analyses at a core laboratory after the end of the study.

## 8.2. Safety assessments

The safety of convalescent plasma will be assessed through standard clinical observation during and after transfusion of the product. Any event will be registered on the adverse event form and in the case of a severe adverse event the principal investigator will be contacted.

In standard clinical practice patients are observed for 1 hour after infusion of plasma products, and the majority of adverse reactions will occur within this timeframe. However, a delayed adverse event can present and will be registered accordingly.

# 8.3. Adverse Events (AEs), Serious Adverse Events (SAEs), and safety reporting

The general definitions of adverse events (AEs) and serious adverse events (SAEs) can be found in Appendix 3. Serious adverse events of special interest are described in Appendix 4: "Definitions of transfusion reactions".

AEs will be reported by the participant (or, when appropriate, by a caregiver, surrogate, or the participant's legally authorized representative).

The investigator and qualified staff at the nursing homes are responsible for detecting, documenting, and recording events that meet the definition of an AE or SAE and remain responsible for following up all AEs.

The study site will record AEs and SAEs is in the adverse events form as a part of the CRF. Both intensity and causality (related to transfusion/study intervention) of the event should be evaluated (Appendix 3).

## 8.3.1. Frequency for Collecting AE and SAE Information

All SAEs will be collected from the start of intervention until the end of the study period (day 60). Medical occurrences that begin before the start of study intervention but after obtaining informed consent will be recorded as Medical History/Current Medical Conditions, not as AEs.

All SAEs will be recorded and reported to the medical monitor immediately and under no circumstance should this exceed 24 hours. The investigator will submit any updated SAE data to the sponsor within 24 hours of it being available.

Investigators are not obligated to actively seek information on AEs or SAEs after conclusion of the study participation. However, if the investigator learns of any SAE, including a death, at any time after a participant has been discharged from the study, and he/she considers the event to be reasonably related to the study intervention or study participation, the investigator must promptly notify the sponsor.

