# **3. Objectives and Endpoints**

Objectives	Endpoints
Primary	
Assess the effect of convalescent plasma on mortality in COVID-19	Primary endpoint: All-cause mortality within the first 28 days of observation. Secondary endpoints: All-cause mortality within 60 days of observation.
Secondary	
Effect of convalescent plasma on recovery time in patients with active COVID-19 infection	Time from intervention to negative SARS-CoV-2 PCR during a 28 day observation period
Effect of convalescent plasma on clinical progression of COVID-19 disease	Requirement of oxygen therapy at days 1, 3, 7, 14, 21 and 28 compared to baseline Change in NEWS score at days 1, 3, 7, 14, 21 and 28 compared to baseline
Exploratory	
Effect of convalescent plasma on biomarkers in COVID-19	Change in CRP and lymphocyte count at day 1, 3, 7 and 14 in the study period. Time to normalized CRP and lymphocyte count
Safety of convalescent plasma in COVID-19	Incidence of adverse events

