# 7. Discontinuation of Study Intervention and Participant Discontinuation/Withdrawal

## 7.1. Discontinuation of Study Intervention

In this study there is only one intervention performed (plasma transfusion) directly after the informed consent has been obtained.

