# 10.3. Appendix 3: AEs and SAEs: Definitions and Procedures for Recording, Evaluating, Follow-up, and Reporting

#### **10.3.1. Definition of AE**

#### **AE Definition**

- An AE is any untoward medical occurrence in a clinical study participant, temporally associated with the use of study intervention, whether or not considered related to the study intervention.
- NOTE: An AE can therefore be any unfavorable and unintended sign (including an abnormal laboratory finding), symptom, or disease (new or exacerbated) temporally associated with the use of study intervention.

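### AE and SAE collection is tied to the start and use of a transfusion that only one arm receives, so non-fatal safety events are not collected on the same basis in both arms

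*Protocol*

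**What the plan says.** Section 8.3.1 sets the collection window: "All SAEs will be collected from the start of intervention until the end of the study period (day 60"). It then says of events which "begin before the start of study intervention but after obtaining informed consent will be recorded as Medical History/Current Medical Conditions, not as AEs". The start of collection for non-serious AEs is not stated separately; it follows from this second sentence and from the definition in 10.3.1: "An AE is any untoward medical occurrence in a clinical study participant, temporally associated with the use of study intervention".

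Section 7.1 says what the intervention is: "In this study there is only one intervention performed (plasma transfusion) directly after the informed consent has been obtained". Under 4.1 the control arm receives local standard supportive treatment alone.

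Other safety provisions lean the same way. Under 8.2, safety is "assessed through standard clinical observation during and after transfusion of the product". Sections 8.3 and 10.3.3 grade causality against the transfusion. The first aggregated safety review in 10.1.4 covers participants who have been dosed.

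Against this, the protocol title (1.1) sets out to evaluate safety as well as efficacy against standard care. The safety endpoint in Section 3 is "Incidence of adverse events", listed as exploratory.

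**The concern.** A comparison of AE incidence between randomised arms needs the same start, end, definition and ascertainment in each arm. Here the start and the definition both refer to something that happens in one arm only.

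Three groups are affected:

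- Controls have no stated start of collection.
- Plasma patients lose any event between consent and transfusion to medical history.
- Patients randomised to plasma but never transfused have no start of intervention either. Section 7.3 recognises that some randomised participants will not get the intervention.

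At stake is the interpretation of hospitalisation, disability and other non-fatal events, both in the final report and in the DMC reviews planned in 9.4. Section 2.3.1 names antibody-dependent enhancement as a theoretical risk. Enhancement would look like worse COVID-19, so judging it depends on a control rate gathered in the same way. The trial is open-label (6.2), so site staff know who was transfused, and unclear rules leave room for different reporting by arm.

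**Working it through.** **Rules side by side**

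| Element | Plasma arm | Control arm |
|---|---|---|
| Start of SAE collection (8.3.1) | Transfusion | Not defined; day 0 implied by the schedule (1.2) |
| Events after consent, before that start (8.3.1) | Medical history | No matching rule |
| AE definition (10.3.1) | Timing relative to use of the intervention | Not met on its wording |
| Relatedness route from disease-related event to AE/SAE (8.3.5) | Open | Closed |
| First aggregated safety review (10.1.4) | Dosed patients | Not covered |
| Deaths (8.1) | Registry | Registry |

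Only the last row is the same for both arms.

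**Number per arm.** The plan's sample size reproduces with the Schoenfeld formula at two-sided 5% and 80% power:

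- Events: 4 × (1.960 + 0.842)² / (ln 0.60)² = 120.3, rounded up to 121.
- Patients: mean mortality is (0.30 + 0.18)/2 = 0.24, and 120.3/0.24 = 501.3, rounded up to 502.
- With the interim analysis: 502 × 1.008 = 506, or 253 per arm at 1:1.

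The concern does not touch this calculation.

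**Length of the gap.** The Synopsis allows plasma up to 2 days after randomisation in the row on intervention group and duration. In the row on the participants' timeframe, randomisation and transfusion follow enrolment at once, and 7.1 also places transfusion directly after consent. These statements disagree. I take 1 to 2 days as an assumption; if transfusion always followed at once, the gap would be close to zero.

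**Illustrative size, using deaths.** The documents give no rate for non-fatal events, so deaths serve as a yardstick. The gap precedes plasma, so the standard-care rate is used for both arms. With a constant hazard h over 28 days and 28-day mortality m:

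- h = −ln(1 − m)/28. For m = 0.30, h = 0.3567/28 = 0.01274 per day.
- Probability of death in the first t days: 1 − exp(−h·t).
- t = 1: 0.0127, and 0.0127 × 253 = 3.2 patients.
- t = 2: 0.0252, and 0.0252 × 253 = 6.4 patients.
- Share of the 0.30 × 253 = 75.9 expected 28-day deaths: 3.2/75.9 = 4% and 6.4/75.9 = 8%.

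Over the 20% to 50% control mortality in Table 1, the range runs from 2.0 patients (20%, 1 day) to 12.2 patients (50%, 2 days).

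**Direction.** If sites take day 0 for controls as randomisation, early control events count and the matching plasma events do not, which flatters plasma. If sites follow the AE definition closely, control events are under-reported, which counts against plasma. The text does not settle which applies, and sites could differ.

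**The case against.** The strongest reply is that the protocol often uses the intervention as a time origin for everyone. Section 4.1 follows participants to 60 days after it, 5.1 sets eligibility relative to it, and the PCR endpoint in Section 3 runs from it. The schedule in 1.2 has one day 0 column and one AE/SAE review row, neither split by arm, and 8.3 has sites record events without limiting this to one arm. This stands. A reader might infer that controls would contribute no SAEs at all, or that the safety question cannot be answered. The documents do not support either inference: control events were evidently meant to be collected.

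Nor does it follow that each expected death in the plasma arm becomes a recorded SAE. Pre-transfusion events drop out, and 8.3.5 diverts common COVID-19 events, including multiple organ failure, from the AE/SAE process unless they are worse than expected or possibly related to the intervention.

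It is also fair that other randomised data bear on harm. Deaths come from the registry, oxygen therapy is registered in both arms, and the DMC sees all safety data. Transfusion-associated circulatory overload has its own criteria and a 6-hour window in Appendix 4. Safety is an exploratory endpoint, and only the title states the comparison outright.

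These points narrow the concern but do not remove it. A shared day 0 that is implied but undefined does not repair the AE definition, the medical-history rule, the transfusion-based assessment in 8.2 or the dosed-only first review. An SAP can decide how to tabulate events but cannot recover events that were never collected.

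**Conclusion.** The point holds for AE incidence and non-fatal SAE incidence. Under the written rules these are not collected on the same basis in both arms, and the promised comparison with standard care is open to bias of unknown direction. It does not hold for mortality at 28 or 60 days.

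The part that can be sized is modest: about 3 to 6 deaths per arm in a gap of 1 to 2 days, or 4% to 8% of 28-day deaths. This assumes a constant hazard, 30% 28-day mortality and 253 patients per arm. Those deaths stay in the primary endpoint; what is at issue is whether they appear as SAEs in the safety tables. The effect on non-fatal events cannot be computed from the protocol. This should be corrected, but it does not threaten the primary analysis.

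**What to change.** - In 8.3.1, collect AEs and SAEs from randomisation to day 60 in both arms at the same visits, and limit medical history to events that began before randomisation. This also gives controls, and patients never transfused, a defined start.
- In 10.3.1, define an AE as any untoward occurrence after randomisation, without reference to use of the intervention.
- Tabulate AE and SAE incidence as randomised, and keep the Appendix 4 transfusion reactions as a plasma-only listing.
- Reconcile the statements in the Synopsis and 7.1 on the time from randomisation or enrolment to plasma.

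The cost is changed protocol and CRF wording and more AE and SAE forms from control patients. Many of the serious ones will concern deaths and hospital transfers that the site already knows about.

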## 8.3.2. Method of Detecting AEs and SAEs

Care will be taken not to introduce bias when detecting AEs and/or SAEs. Open-ended and non-leading verbal questioning of the participant is the preferred method to inquire about AE occurrences.

## 8.3.3. Follow-up of AEs and SAEs

After the initial AE/SAE report, the investigator is required to proactively follow each participant at subsequent visits/contacts. All SAEs will be followed until resolution, stabilization, the event is otherwise explained, or the participant is lost to follow-up.

## 8.3.4. Regulatory Reporting Requirements for SAEs

Prompt notification by the investigator to the sponsor of an SAE is essential so that legal obligations and ethical responsibilities towards the safety of participants and the safety of a study intervention under clinical investigation are met.

The sponsor has a legal responsibility to notify both the local regulatory authority and other regulatory agencies about the safety of a study intervention under clinical investigation.

An investigator who receives an investigator safety report describing an SAE or other specific safety information (e.g., summary or listing of SAEs) from the sponsor will review and then file it.

# 8.3.5. Disease-Related Events and/or Disease-Related Outcomes Not Qualifying as AEs or SAEs

The following disease-related events (DREs) are common in participants with COVID-19 and can be serious/life threatening:

- Fever and/or chills
- Need for increased oxygenation or ventilation support
- Persistent pain or pressure in the chest
- New-onset confusion
- Multiple organ dysfunction or failure

Because these events are typically associated with the disease under study, they will not be reported according to the standard process for expedited reporting of SAEs even though the event may meet the definition of an SAE. These DREs will be followed by the medical monitor and recorded by the site designee for later evaluation by the Data Monitoring Committee (DMC).

NOTE: However, if either of the following conditions applies, then the event must be recorded and reported as an AE/SAE (instead of a DRE):

The event is, in the investigator's opinion, of greater intensity, frequency, or duration than expected for the individual participant.

OR

The investigator considers that there is a reasonable possibility that the event was related to study intervention.

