#### **Transfusion reactions-Definitions**

## TRALI (Transfusion associated acute lung injury)

In patients with no evidence of acute lung injury (ALI) prior to transfusion, TRALI is

diagnosed if a new ALI is present (all five criteria should be met):

- Acute onset
- Hypoxemia
- $o Pa0_2 / Fi0_2 < 300 mm Hg or$
- o Oxygen saturation is < 90% on room air or

o Other clinical evidence

Bilateral infiltrates on frontal chest radiograph

No evidence of left atrial hypertension (i.e. circulatory overload)

No temporal relationship to an alternative risk factor for ALI,

during or within 6 hours of completion of transfusion.

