## Acute hemolytic transfusion reaction (AHTR)

An AHTR has its onset within 24 hours of a transfusion. Clinical or laboratory features of hemolysis are present.

Common signs of AHTR are:

- Fever
- Chills/rigors
- Facial flushing
- Chest pain
- Abdominal pain
- Back/flank pain
- Nausea/vomiting
- Diarrhea
- Hypotension
- Pallor
- Jaundice
- Oligoanuria
- Diffuse bleeding
- Dark urine
- Common laboratory features are:
- Hemoglobinemia
- Hemoglobinuria
- Decreased serum haptoglobin
- Unconjugated hyperbilirubinemia
- Increased LDH an AST levels
- Decreased hemoglobin levels

Not all clinical or laboratory features are present in cases of AHTR.

Blood group serology usually shows abnormal results but absence of immunological findings does not exclude AHTR. AHTR may also be due to erythrocyte auto-antibodies in the recipient or to non immunological factors like mechanical factors inducing hemolysis (malfunction of a pump, of a blood warmer, use of hypotonic solutions, etc.).

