## Transfusion associated circulatory overload (TACO)

TACO is characterized by any 4 of the following:

- Acute respiratory distress
- Tachycardia
- Increased blood pressure
- Acute or worsening pulmonary edema on frontal chest radiograph
- Evidence of positive fluid balance

Occurring within 6 hours of completion of transfusion. An elevated BNP is supportive of TACO.

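### Section 8.3.5 exempts signs shared with transfusion reactions without any time limit, so a reaction not recognised as one stays a disease-related event

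*Protocol*

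**What the plan says.** Section 8.3.5 lists five events as common in COVID-19. Three matter here: "Fever and/or chills", "Need for increased oxygenation or ventilation support" and "Persistent pain or pressure in the chest". The other two are new confusion and multiple organ failure. The section says that these events "will not be reported according to the standard process for expedited reporting of SAEs", even where they meet the SAE definition. The Medical Monitor follows them, and the site records them for the DMC to consider later. A NOTE reverses this, and the event becomes an AE or SAE, if the investigator finds it worse than expected for that patient or sees a reasonable possibility of a link to the intervention.

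Appendix 4 defines the transfusion reactions, which Section 8.3.6 makes adverse events of special interest (AESIs), and gives them time windows. For acute haemolytic reaction (AHTR): "An AHTR has its onset within 24 hours of a transfusion". For TRALI: "during or within 6 hours of completion of transfusion". For TACO: "Occurring within 6 hours of completion of transfusion". Section 8.3.5 refers neither to these windows nor to Appendix 4.

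Section 6.1 requires one hour of close observation after transfusion. It also says that serious events under Section 8.3.5 go immediately to the Medical Monitor.

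**The concern.** Acute reactions to plasma are the safety signal most specific to this intervention, and the risk table in Section 2.3 says that the elderly are at higher risk of transfusion complications. In the first hours after transfusion, a patient with active COVID-19 who becomes febrile or needs more oxygen may have either condition. If nobody connects the event with the plasma, Section 8.3.5 classes it as disease-related.

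Two things then depend on that classification. The safety endpoint in Section 3 is the incidence of adverse events, and the heading and NOTE of 8.3.5 treat a disease-related event as an alternative to an AE. The stop or pause review in Section 10.1.4 names deaths, SAEs and AESIs, but not disease-related events.

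**Working it through.** No sample size, power or error rate enters this point, and the protocol states no figure to reproduce. The check sets the two lists side by side.

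| Event in 8.3.5 | Counterpart in Appendix 4 | Window |
|---|---|---|
| Fever or chills | AHTR: both named | 24 h |
| Increased oxygen or ventilation need | TRALI: hypoxemia; TACO: acute respiratory distress | 6 h; 6 h |
| Persistent chest pain or pressure | AHTR: chest pain named | 24 h |
| New-onset confusion | none listed | – |
| Multiple organ dysfunction or failure | none listed | – |

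**Overlap.** Three of five categories overlap. Two share a named sign. Oxygen need is an inference, since Appendix 4 lists hypoxemia and respiratory distress rather than the need itself.

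**Time.** Close observation lasts 1 hour (Section 6.1). Counting from the end of transfusion, 6 − 1 = 5 hours of the TRALI and TACO windows and 24 − 1 = 23 hours of the AHTR window lie beyond it. For AHTR this is approximate, because Appendix 4 does not say whether its 24 hours run from the start or the end of transfusion. The next scheduled assessment is day 1.

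**Who detects the event in those hours.** Section 8.3 relies on reports from the participant or a caregiver and on nursing-home staff. Section 5 notes a high proportion of dementia. TRALI requires bilateral infiltrates on a chest radiograph, and the Schedule of Activities has no radiograph. Haptoglobin, bilirubin, LDH and AST, which are AHTR features, are in neither the scheduled blood tests nor the care-home panel of Appendix 2. Hemoglobin is in both.

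**The two routes out of 8.3.5.** Both conditions of the NOTE are the investigator's judgement, and neither refers to time since transfusion. The AESI and hemovigilance route in 8.3.6 starts only once an event has been identified as an Appendix 4 reaction. Neither route catches an event that nobody links to the plasma.

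**Comparison between arms.** The causality condition can operate only in the plasma arm, since controls receive no plasma. The same symptom on day 0 or 1 can therefore be an AE in one arm and a disease-related event in the other.

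**Internal tension.** Section 6.1 has serious 8.3.5 events reported immediately to the Medical Monitor. Section 8.3.5 removes them from expedited reporting and has them recorded for later DMC evaluation. The two can be read together (immediate notice to the Medical Monitor, no expedited SAE report), but the protocol does not say so.

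**The case against.** A reader might infer that plasma reactions will be filed as COVID-19 by default, and that the Medical Monitor will hear of them late. The documents do not support either reading.

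- The NOTE makes AE or SAE reporting mandatory when a link to plasma is reasonably possible. The causality scale in Appendix 3 rates indeterminate evidence as *Possible*. An investigator who weighs the question and cannot tell the causes apart should therefore report the event. The trial is open-label, so staff know who was transfused.
- Section 6.1 gives the Medical Monitor immediate notice of serious 8.3.5 events, and 8.3.5 itself has the Medical Monitor follow them.
- One shared symptom is not a reaction. TRALI needs all five of its criteria, TACO needs four of five, and AHTR needs features of hemolysis.
- The exemption concerns expedited SAE reporting. Non-serious fever was never subject to it.
- Section 8.2 says that any event goes on the adverse event form, including delayed ones.

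The first four stand, and they confine the point to reactions that are not recognised. The last stands in part. If 8.2 governs, a disease-related event may still reach the AE form. But 8.3.5 says in its heading that these events do not qualify as AEs, and its NOTE makes the two categories exclusive. A list of disease-related events with a causality override is a legitimate design. The weakness is only that this override is not tied to windows that the protocol has already defined.

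**Conclusion.** The point holds in a narrow form. Suspected reactions are adequately routed. A reaction not recognised as one remains a disease-related event and, on the terms of 8.3.5, falls outside the AE incidence endpoint and the death, SAE and AESI review list, unless it is fatal or is reclassified later. The overlap is three of five exempt categories, over 6 hours for TRALI and TACO and 24 hours for AHTR.

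The number of events affected cannot be estimated from the protocol, which gives neither a reaction rate nor a share that would be missed. The conclusion assumes that 8.3.5, rather than the broader sentence in 8.2, decides what is counted as an AE. It is a worthwhile and cheap improvement to safety reporting. It does not touch the mortality endpoint.

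**What to change.** Add to the NOTE in Section 8.3.5, in substance: *The exemption does not apply to a listed event that is new or worsening and has its onset within the Appendix 4 windows, up to 24 hours after transfusion. Such an event is recorded as an AE, or as an SAE under Section 8.3.1 if serious, and is checked against Appendix 4.*

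Apply the same period from day 0 in the control arm and tabulate it separately by arm. Controls have no transfusion time, so the text must name a clock start for them, such as the day 0 assessment.

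Reconcile Section 6.1 with 8.3.5 by stating what is reported to whom, and when, for a serious disease-related event. State also whether such an event goes on the AE form under Section 8.2.

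The cost is a short text change and some COVID-19 symptoms with onset on days 0 to 1 reported as AEs in both arms. Limiting the rule to new or worsening events matters, because patients are enrolled while symptomatic. The change concerns how events are recorded and leaves treatment as it is.
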